Exploratory Aim 2: Two new screening measures, MAPI and Berlin, have been used extensively as screening measures for sleep apnea in the general population, however little is known about their diagnostic capabilities in TBI patients undergoing inpatient rehabilitation. This study proposes to explore the diagnostic accuracy of these screening tools within this specific population. (ADD ANY OTHER DETAILS/JUSTIFICATION) Analytical Plan: Receiver operator curve (ROC) analyses will be conducted for MAPI and Berlin each. This will provide estimates of sensitivity and specificity for all possible cut-points on the MAPI and Berlin. Of particular interest is to identify sufficiently high sensitivity without compromising too much specificity (e.g., 90% SE and SP no smaller than 60%). All analyses will be performed using SAS v.9.4 (SAS Institute Inc., Cary, NC).

References

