	
Exclusion Criteria:
 
 
*Habitual sleep duration > 2 hours/night for two (2) consecutive nights not being established prior to PSG
 
*Presence of a physical deformity precluding sensitivity of PSG instrumentation (i.e. full body cast, PSG that could not be removed prior to PSG)
 
*Medical instability as determined by the treating physician (i.e. agitation, acute illness)
 
*Infeasibility of tracheostomy placement with decannulation or overnight capping during rehabilitation
 

Study Product
	
Aim1: Subjects will complete paper and pencil screening tests (STOPBang, Berlin, MAPI), actigraphy, and Level 1 Diagnostic Polysomnography.
 
Aim 2: Subjects recruited will undergo simultaneous administration of Level 1 Diagnostic Polysomnography and Level 3 Portable Diagnostic tests.

Statistical Methodology
	
Aim 1: Area under the curve (AUC) of screening tools predicting sleep apnea status and severity.
 
Aim2: Non-inferiority of Level 3 portable diagnostic tests to the criterion standard, Level 1 Polysomnography.

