**Product Description and Intended Use:****Sleep Apnea Screening Tools (comparators)**

STOPBANG (OSA Screening Comparator). The STOPBANG is comprised of eight (8) items that refer to Snoring, Tiredness, Observed breathing pauses during sleep, treatment for high blood Pressure, elevated Body mass index, older Age, wide Neck circumference, and male Gender. An affirmative response to 2 items indicates low risk, 3-4 items intermediate risk, 5-8 items high risk.

Berlin (OSA Screening Comparator). The Berlin Questionnaire is a 10-item measure that evaluates risk factors for sleep apnea into three (3) categories (snoring severity, excessive daytime sleepiness and history of high blood pressure or obesity). Positivity in two or more of these categories is associated with a high likelihood of clinically-relevant sleep apnea.

Multivariate Apnea Prediction Index (MAPI; OSA Screening Comparator). The questionnaire consists of three breathing-related questions and utilizes information on demographics (sex, weight, height, age), from which a probability of having sleep apnea (0-100%) can be calculated.

Actigraphy (ACG; Comparator). A wrist-worn accelerometer (Actiwatch Spectrum, Philips/Respironics, Bend, OR) was used to document sleep metrics during the trial. Activity data informing sleep statistics were recorded in 15-second intervals.

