### **Sample Size Justification**

Power Analyses from Research Plan:

(Aim 1) To test the hypothesis for Aim 1, a paired-sample diagnostic analysis (estimated sensitivities/specificities) for each screening measure relative to the criterion standard, Level 1 PSG) was

performed using the same sample of patients. Prevalence of sleep apnea (as determined by Level 1 PSG) was conservatively estimated to be 30% using investigators' published reports of 37-39% prevalence in acute rehabilitation TBI samples. A two-sided McNemar's test, assuming a significance level of  $\alpha = 0.05$ , will have at least 80% power to detect a difference in sensitivities of 20% between screening measures for a sample size of 237. The power of the test will increase if the prevalence is higher than 30% (e.g., a prevalence of 35% would yield 87% power with 237 subjects and only require 203 subjects for 80% power). Furthermore, a sample size of 237 will have at least 80% power to detect a difference of 20% in sensitivities between screening measures in detecting sleep apnea.

(Aim 2) To test the non-inferiority hypothesis of the portable device for diagnosing sleep apnea, the non-inferiority of SE and SP (relative to SEH = 0.9 and SPH = 0.6, each within  $\Delta = 0.1$ ) were jointly tested at the significance level of  $\alpha=0.05$  by estimating the cross-product of two one-sided  $1-\alpha^*$  confidence intervals; SEH and SPH were selected a priori and were considered sufficiently large to obviate the need Level 1 PSG. For the purposes of the clinical trial, the study was powered to demonstrate non-inferiority of Level 3 sleep studies relative to fixed values of sensitivity (SE) and specificity (SP). Minimum sample sizes of 83 and 153 patients achieved at least 80% power to detect non-inferiority of SE to 90% and SP to 60% with a non-inferiority limit of  $\Delta = 0.1$ , using one-sided exact tests each at a 5% level of significance. In total, 214 subjects were available for analysis which yields 83.9% and 98.8% power, respectively, when testing the non-inferiority of SE and SP each at a 2.53% level of significance and maintaining a 5% level of significance when testing SE and SP jointly.

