Diagnosis and Main Inclusion Criteria	
Inclusion Criteria:
 
 *Damage to brain tissue caused by an external mechanical force *Alteration of consciousness > 24 hours, or loss of consciousness > 30 minutes, or Glasgow Coma Scale (GCS) score in the Emergency Department of 3-12, or intracranial abnormalities on imaging regardless of GCS *Admission to inpatient rehabilitation *Minimum age 16 years at civilian sites and 18 years at the VA site *Consent to participate by person with brain injury (if able), family member or legally authorized representative into the TBI Model System lifetime study. This criterion was relaxed in Study Month 11.

	
Exclusion Criteria:
 
 *Habitual sleep duration > 2 hours/night for two (2) consecutive nights not being established prior to PSG *Presence of a physical deformity precluding sensitivity of PSG instrumentation (i.e. full body cast, PSG that could not be removed prior to PSG) *Medical instability as determined by the treating physician (i.e. agitation, acute illness) *Infeasibility of tracheostomy placement with decannulation or overnight capping during rehabilitation

Study Product
	
Aim1: Subjects will complete paper and pencil screening tests (STOPBang, Berlin, MAPI), actigraphy, and Level 1 Diagnostic Polysomnography.
 
Aim 2: Subjects recruited will undergo simultaneous administration of Level 1 Diagnostic Polysomnography and Level 3 Portable Diagnostic tests.

Statistical Methodology
	
Aim 1: Area under the curve (AUC) of screening tools predicting sleep apnea status and severity.
 
Aim2: Non-inferiority of Level 3 portable diagnostic tests to the criterion standard, Level 1 Polysomnography.

Statistical and Power Considerations

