
Data analysis plan specific to each aim. The analytic methods designed *a priori* for each hypothesis are detailed below. Reporting of findings will strictly adhere to the requirements of the STARD guidelines.

Aim 1 (Hypothesis 1.1): *Sensitivity and specificity of actigraphy will be superior compared to clinical prediction rules (i.e., STOP-Bang) for determining risk of sleep apnea as diagnosed by Level 1 polysomnography in TBI patients undergoing inpatient rehabilitation.* **Justification of Assumptions/Power Estimate:** To test hypothesis 1.1, a paired-sample diagnostic analysis will be performed as the estimated sensitivities/specificities for STOPBang and ACG (each versus the reference gold standard, Level 1 PSG) will be estimated using the same sample of patients. Prevalence of sleep apnea (as determined by Level 1 PSG) is conservatively estimated to be 30% using investigators' published reports of 37-39% prevalence in acute rehabilitation TBI samples.¹⁻² A two-sided McNemar's test, assuming a significance level of $\alpha = 0.05$, will have at least 80% power to detect a difference in sensitivities of 20% between ACG and STOPBang if the total sample size is at least 237 patients. The power of the test will increase if the prevalence is higher than 30% (e.g., a prevalence of 35% would yield 87% power with 237 subjects and only require 203 subjects for 80% power). Furthermore, a sample size of 237 will have at least 80% power to detect a difference of 20% in sensitivities between actigraphy and STOP-Bang in detecting sleep apnea. **Analytic Plan:** The sensitivity (SE) and specificity (SP) of both STOPBang and ACG will be estimated using Level 1 PSG as the reference gold standard. As STOPBang and ACG are measured on an interval scale, and are not

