dichotomous, pre-specified cut-points for each screening tool will be used to classify a subject as being at high risk for sleep apnea. We expect that STOPBang values > 5 and abnormal ACG total sleep time (< 5 hours with desaturation) will produce sufficiently high SEs with reasonable tradeoff in SP (noting that SE and SP are inversely related). Similarly, for Level 1 PSG, a diagnosis of sleep apnea will be made if $AHI \geq 5$. Cross-tabulations of STOPBang and ACG screening for high risk of sleep apnea (positive/negative) versus Level 1 PSG diagnosis (positive/negative) will be constructed and estimates of diagnostic accuracy (i.e., sensitivity, specificity, positive and negative predictive values, and diagnostic accuracy, ROC curves, AUC) will be estimated along with 95% confidence intervals. To address hypothesis 1.1, two-sided McNemar's tests will be used to compare the paired SEs and paired SPs between STOPBang and ACG assuming a significance level of $\alpha = 0.05$. All analyses will be performed using SAS v.9.4 (SAS Institute Inc., Cary, NC).

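### The SAP's only actigraphy cut-point for Hypothesis 1.1 adds a desaturation condition that the actigraph as described does not record and no section defines

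*SAP*

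**What the plan says.** The SAP's Aim 1 hypothesis is "Sensitivity and specificity of actigraphy will be superior compared to clinical prediction rules", with STOPBang as the named rule. Its Analytic Plan says that cut-points fixed in advance will dichotomise each tool, and that two-sided McNemar "tests will be used to compare the paired SEs and paired SPs between STOPBang and ACG" at the 5% level. The only actigraphy cut-point given is "abnormal ACG total sleep time (< 5 hours with desaturation". It is worded as an expectation of good sensitivity, but it directly follows the statement that pre-specified cut-points will be used.

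The protocol's section on screening tools describes the actigraph as a wrist-worn accelerometer: "Activity data informing sleep statistics were recorded in 15-second intervals". Its Diagnostic Comparators section lists pulse oximetry for the Level 1 PSG and for the Level 3 device. The data collection section mentions oximetric data again, for the Level 3 recordings.

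The Study Summary lists for Aim 1: "Subjects will complete paper and pencil screening tests (STOPBang, Berlin, MAPI), actigraphy, and Level 1 Diagnostic Polysomnography". Level 3 testing appears under Aim 2: "Subjects recruited will undergo simultaneous administration of Level 1 Diagnostic Polysomnography and Level 3 Portable Diagnostic tests". The SAP's missing-data text does name Level 3 PSG among the data needed for the primary hypotheses taken together.

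The protocol's Statistical Analysis Plan section, written in the past tense, examines actigraphy as 12 hours minus total sleep time at hourly cut points from 3 to 10 hours. It has no desaturation term.

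**The concern.** Hypothesis 1.1 is about actigraphy. A paired McNemar test needs every subject classified positive or negative by actigraphy, and the only rule supplied asks for a physiological signal that the device is not described as recording. The word desaturation occurs nowhere else in either document, so its depth, duration, frequency and source are all open.

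At stake is what the planned test would evaluate. If oximetry is borrowed from a sleep study, a sleep study must already have been done before the screening tool can be scored, and any advantage over STOPBang may belong to the oximetry. If it is borrowed from the Level 1 recording, the index test and the reference are no longer separate. The SAP also commits to STARD reporting, so a reader should be able to see how index-test positivity was defined.

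**Working it through.** **1. Possible sources of desaturation**
- *Actigraph.* Activity only, as described. The rule cannot be computed.
- *Level 3 device.* Oximetry is described and the recording was simultaneous with the PSG. The rule can be computed, but the index test combines two devices and borrows from the Aim 2 index test.
- *Level 1 PSG.* Oximetry is described. The rule can be computed, but as a composite that shares a signal with the recording that yields the reference apnea-hypopnea index (AHI). That is the setting for incorporation bias.

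Within Aim 1 as listed in the Study Summary, the only oximetry belongs to the reference. Because the missing-data text names Level 3 PSG, the Level 3 branch cannot be ruled out.

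**2. Direction of the added condition**

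Let T be total sleep time below 5 hours and D be desaturation, and read the rule as T and D. Compared with T alone:
- change in sensitivity = −P(T and not D | apnea) ≤ 0
- change in specificity = +P(T and not D | no apnea) ≥ 0

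So the condition can only lower or keep sensitivity and raise or keep specificity. The documents give no frequencies for T or D, so these shifts cannot be sized. Nor can incorporation bias, which would be the difference between using Level 1 desaturation and using desaturation from an independent source.

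**3. The SAP's power figure, then the Level 3 branch**

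Inputs from the SAP's power paragraph: two-sided 5% test, a 20-point sensitivity difference (d = 0.20), 30% prevalence, and at least 80% power "if the total sample size is at least 237 patients". The discordant proportion ψ is not given. With the normal approximation and n apnea patients:

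power = Φ[(d√n − 1.96√ψ) / √(ψ − d²)]

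- Back-solving ψ: n = 237 × 0.30 = 71.1 and 80% power give ψ = 0.375. Check: (0.20 × 8.432 − 1.96 × 0.612) / √0.335 = 0.84, and Φ(0.84) = 0.80.
- The SAP's 35% figures: n = 203 × 0.35 = 71.05 gives 80% (stated 80%). n = 237 × 0.35 = 82.95 gives 86% (stated 87%). The small gap is consistent with a different variant of the test: exact McNemar with ψ = 0.34 gives 80.5% at n = 71 and 86.9% at n = 83.
- ψ is an assumption. Over ψ = 0.20 to 0.50, the total needed at 30% prevalence runs from 123 to 320.

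The protocol's Sample Size Justification says for Aim 2: "In total, 214 subjects were available for analysis". Assume that Level 3 oximetry exists only in those 214, and keep ψ = 0.375:
- 30% prevalence: n = 214 × 0.30 = 64.2, power about 76%
- 35% prevalence: n = 214 × 0.35 = 74.9, power about 82%

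**4. Is 5 hours already on the protocol's grid?**

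12 − 5 = 7. Total sleep time below 5 hours is the same as 12 hours minus total sleep time above 7 hours, and 7 is one of the eight cut points from 3 to 10.

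**The case against.** The strongest objection is that the rule may never have mattered. The protocol names the area under the ROC curve as the Aim 1 primary endpoint and describes, in the past tense, an actigraphy analysis on sleep time alone. The SAP introduces the cut-point as an expectation, and the desaturation words may be a loose remark. Much of this stands. Nothing shows that the rule was applied, and the protocol's own analysis is untouched. It does not remove the gap: the SAP gives no other actigraphy cut-point, so without this one its McNemar test has no actigraphy classification.

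A reader might infer that the actigraphy results carry incorporation bias. The documents do not support that: the bias arises only if Level 1 oximetry was used, and no section says it was.

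A reader might also infer that the comparison is underpowered. That is not supported either. The fall to about 76% occurs only in the Level 3 branch at a prevalence that the SAP calls conservative against reported rates of 37–39%, and the SAP itself says 203 subjects suffice at 35%. The 214 is an Aim 2 analysis count, not a count of usable oximetry. Nor can one take the planned 20-point difference as belonging to sleep time alone and subtract from it, because the SAP states it for actigraphy as that plan classifies it.

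Finally, one may object to changing a cut-point called pre-specified after results are published. That is a fair cost, and it is why the change must be disclosed as post hoc.

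**Conclusion.** The concern holds for the SAP's planned McNemar test of Hypothesis 1.1 and no further. Followed as written, the actigraphy rule cannot be scored from actigraphy, or it turns the index test into a two-device composite, which with Level 1 oximetry would also share a signal with the reference. It also disagrees with the protocol's analysis of sleep time alone.

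This rests on the documents' description of the devices. Confidence is high on the textual gap. The size and net direction of any incorporation bias are unknown. The possible loss of power in the Level 3 branch is secondary and disappears at 35% prevalence under the assumed discordance. The point should be fixed, because it leaves the index test of a primary hypothesis undefined and the repair is cheap.

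**What to change.** Reconcile the SAP's Aim 1 Analytic Plan with the protocol's Statistical Analysis Plan section in a dated, disclosed clarification. It must be labelled post hoc: participants finished in 02/2019, and the SAP carries the date September 16, 2020.

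- Define actigraphy positivity for Hypothesis 1.1 on actigraphy data alone: total sleep time below 5 hours, that is, 12 hours minus total sleep time above 7 hours.
- State whether desaturation was ever used in classifying actigraphy.
- If it was, give the device and threshold, report the comparison with and without it, and label the version with it as a composite test, not actigraphy.
- If it was not, say that no Level 1 or Level 3 signal entered the classification.

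The cost is a short text and, only if desaturation was used, a re-run cross-tabulation and its McNemar tests; no new data are needed. The downsides are a disclosed change to a cut-point called pre-specified and possibly a lower specificity for actigraphy (step 2 of the working). The change does not settle the separate difference between the SAP's McNemar tests and the protocol's comparison of areas under the curve.

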(Aim 2: Hypothesis 2.1): *Level 3 portable polysomnography with greater consumer accessibility will be equivalent (non-inferior) to the less accessible Level 1 polysomnography in determining presence of sleep apnea in TBI patients undergoing inpatient rehabilitation.* Justification of Assumptions/Power Estimate: To test hypothesis 2.1, the sensitivity (SE) and specificity (SP) of Level 3 PSG (compared to Level 1 PSG, the reference gold standard) will each be estimated and compared to fixed hypothesized rates of SE and SP considered sufficiently large enough to potentially obviate the need for Level 1 PSG. Based on a review of the literature and consensus among the investigators in this study, SE and SP no worse (non-inferior) to 90% and 60%, respectively, are considered sufficiently large enough. To test for non-inferiority of the SE to 90% and the SP to 60%, a non-inferiority threshold of $\Delta = 0.1$ is assumed for both measures. A sample size of at least 83 patients is necessary to achieve a minimum of 80% power to test the non-inferiority of the SE to 90% (assuming $\Delta = 0.1$ and $\alpha = 0.05$). A sample size of at least 153 patients is necessary for a minimum of 80% power to test the non-inferiority of the SP to 60% (assuming $\Delta = 0.1$ and $\alpha = 0.05$). Thus, a total of 153 subjects is required to sufficiently power both non-inferiority hypotheses. Analytic Plan: To test hypothesis 2.1, the sensitivity (SE) and specificity (SP) of Level 3 PSG (compared to Level 1 PSG, the reference gold standard) will each be estimated and compared to fixed hypothesized rates of SE and SP of 90% and 60%, respectively, considered sufficiently large enough. Level 1 PSG (reference) diagnosis of sleep apnea will be made based on $AHI \geq 5$. Level 3 PSG (test) diagnosis will be made based $AHI \geq 5$. A cross-tabulation of Level 3 PSG (positive/negative) versus Level 1 PSG (positive/negative) will be constructed and standard measures of diagnostic accuracy will be estimated along with 95% confidence intervals (i.e., sensitivity, specificity, positive and negative predictive values, and diagnostic accuracy). To test for non-inferiority of the SE to 90% and the SP to 60%, a non-inferiority threshold of 0.1 is assumed. If the lower bound on the 95% confidence interval for SE is strictly above 80% and the lower bound on the confidence interval for SP is strictly above 50% then non-inferiority of Level 3 PSG (compared to Level 3 PSG) can be established. All analyses will be performed using SAS v.9.4 (SAS Institute Inc., Cary, NC).

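### The SAP sizes Aim 2 at one-sided 5% but judges it on a 95% confidence limit, so specificity at 153 patients has about 70% power, not 80%

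*SAP*

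**What the plan says.** **Sizing (SAP, Aim 2, Hypothesis 2.1, power estimate).** The target is set as "SE and SP no worse (non-inferior) to 90% and 60%, respectively, are considered sufficiently large enough", and "a non-inferiority threshold of $\Delta = 0.1$ is assumed for both measures". The limits to be excluded are therefore 80% for SE and 50% for SP. The SAP then states "A sample size of at least 83 patients is necessary to achieve a minimum of 80% power to test the non-inferiority of the SE", and gives 153 patients for SP on the same terms, both at alpha 0.05 with no sidedness. It concludes: "Thus, a total of 153 subjects is required to sufficiently power both non-inferiority hypotheses".

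**Decision rule (same section, analytic plan).** Non-inferiority is declared "If the lower bound on the 95% confidence interval for SE is strictly above 80" per cent and the lower confidence bound for SP is strictly above 50%. The interval method is not named, and the level is not repeated for SP.

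**Protocol, Sample Size Justification.** The same 83 and 153 are described as obtained "using one-sided exact tests each at a 5% level of significance". The Protocol then gives power at 214 analysed subjects, with each test at 2.53%, as 83.9% and 98.8%.

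**Protocol, Statistical Analysis Plan.** The rule uses 0.0253 per test and lower limits of 94.9% intervals. Neither the 0.0253 level nor the figures at 214 appear in the SAP.

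**The concern.** Power belongs to a particular decision rule. Here the sample size was worked out for one rule and the result will be judged by a stricter one. A 95% interval leaves 2.5% in the lower tail, half the error rate used for the sizing. The SAP's at-least-80% statement therefore does not describe the test it goes on to define.

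What is at stake is interpretation. If a lower limit fell short, a reader trusting the stated 80% would count that more heavily against the portable device than the planned power justifies, above all for SP.

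**Working it through.** **Inputs.** SE: null value p0 = 0.80, assumed true value p1 = 0.90. SP: p0 = 0.50, p1 = 0.60 (SAP, Aim 2). Target power is 80%. Normal quantiles: 1.6449 (one-sided 5%), 1.9600 (one-sided 2.5%), 0.8416 (80% power).

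**Step 1: reproduce the plan's sizes.** One-sample proportion, normal approximation:

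n = [(z_alpha × √(p0(1−p0)) + 0.8416 × √(p1(1−p1))) / 0.1]²

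One-sided 5%:
- SE: [(1.6449 × 0.4 + 0.8416 × 0.3) / 0.1]² = 82.9, so **83**.
- SP: [(1.6449 × 0.5 + 0.8416 × 0.4899) / 0.1]² = 152.5, so **153**.

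One-sided 2.5%:
- SE: [(1.9600 × 0.4 + 0.8416 × 0.3) / 0.1]² = 107.4, so 108.
- SP: [(1.9600 × 0.5 + 0.8416 × 0.4899) / 0.1]² = 193.8, so 194.

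Only one-sided 5% gives the SAP's pair. The Protocol calls the tests exact, but exact one-sided 5% power is 79.5% at 83 and 76.2% at 153, so the sizes come from the approximation.

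**Step 2: power of the SAP's own rule.** At one-sided 2.5%:

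Power = Φ[(0.1√n − 1.9600 × √(p0(1−p0))) / √(p1(1−p1))]

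- SE, n = 83: Φ[(0.9110 − 0.7840) / 0.3] = Φ(0.424) = **66.4%**.
- SP, n = 153: Φ[(1.2369 − 0.9800) / 0.4899] = Φ(0.524) = **70.0%**.
- SE, n = 153 (the SAP's total counted for both tests): Φ[(1.2369 − 0.7840) / 0.3] = Φ(1.510) = **93.4%**.

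**Step 3: dependence on the interval method.** For each method, find the smallest count whose 95% lower limit exceeds p0, then take the binomial probability of reaching that count under p1.

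| Test, n | Formula | Wald | Wilson | Exact |
|---|---|---|---|---|
| SE, 83 | 66.4% | 79.5% (≥73) | 68.4% (≥74) | 68.4% (≥74) |
| SP, 153 | 70.0% | 70.8% (≥89) | 70.8% (≥89) | 65.0% (≥90) |
| SE, 153 | 93.4% | 96.9% (≥131) | 91.5% (≥133) | 91.5% (≥133) |

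SP at 153 misses 80% under every method. SE at 83 misses it clearly under three and only marginally with Wald limits.

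**Step 4: the Protocol's figures at 214.** With z = 1.9548 for 0.0253 and all 214 patients counted in each test:
- SE: Φ[(1.4629 − 0.7819) / 0.3] = Φ(2.270) = 98.8%.
- SP: Φ[(1.4629 − 0.9774) / 0.4899] = Φ(0.991) = 83.9%.

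The Protocol's values are right on this counting, but it prints them in the opposite order for SE and SP.

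**The case against.** **The Protocol already deals with the level.** This is the strongest reply, and much of it stands. The Protocol's 0.0253 per test is practically the SAP's 95% rule, and on its counting both tests exceed 80% power at 214. A reader might infer that Aim 2 as analysed was underpowered; on the documents' own counting that does not follow. What remains is that the SAP's sizing statement is untrue of the SAP's rule and does not match the Protocol.

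**A 95% interval could mean a one-sided 95% bound.** The mismatch would then vanish. But the SAP does not say so, and the same section uses 95% intervals for its ordinary accuracy estimates. The Protocol's 94.9% is 1 − 2 × 0.0253, which is the two-sided convention.

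**A reader might infer that the planned chance of passing both tests was below one half**, from 0.664 × 0.700 = 46%. That needs 83 PSG-positive and 153 PSG-negative patients, 236 in that exact split, which neither document plans. With Wald limits the same split gives 0.795 × 0.708 = 56%. On the SAP's counting of 153 for both tests it is 0.934 × 0.700 = 65%.

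**A reader might also infer that the rule should move to a 90% interval**, the level that was sized. That would contradict the Protocol's 0.0253 rule, and it would relax the success criterion after participants had completed in 02/2019 and results had been published.

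**The rule is conservative.** True: it is stricter than the test that was sized. This bears on severity, not on whether the stated power is correct.

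**Conclusion.** The point holds for the SAP's power statement, at moderate severity. The sizes are one-sided 5% sizes and the decision is made at one-sided 2.5%. SP at 153 has about 70% power (65% to 71% by interval method) against the stated minimum of 80%. SE at 83 has about 66% to 68%, or 79.5% with Wald limits. With all 153 patients counted for both tests, SE is well powered, so the sufficiency claim for 153 fails through SP alone.

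This rests on three assumptions: true values of exactly 90% and 60%; a two-sided reading of the 95% interval, applied to SP as well as SE; and the documents' practice of counting every patient in each test. SE can be estimated only in PSG-positive patients and SP only in PSG-negative ones, so actual denominators would be smaller. That is a separate matter, and nothing here relies on it.

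**What to change.** In the SAP's Aim 2 section:

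- Keep the 95% rule, or adopt the Protocol's 0.0253 per-test rule, which is nearly the same. State the one-sided level explicitly for both SE and SP.
- Restate power at that level: SP about 70% at 153. By the same formula, 80% needs 194 for SP and 108 for SE. Withdraw the statement that 153 is enough for both.
- Carry over the Protocol's figures for 214 as SE 98.8% and SP 83.9%, say that they count all 214 in each test, and correct the order in the Protocol.
- Name the interval method and the denominator for each measure.

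The cost is a wording change in the SAP, a small correction in the Protocol, and a less favourable stated power at 153. No extra patients are needed and the success rule is not relaxed.
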